10.4 ANALYSES SETS

10.4.1 Modified Intent-to-Treat (mITT) Analysis Set

The Modified Intent-to-Treat (mITT) analysis set is a subset of the ITT set. This set will consist of all enrolled subjects who were vaccinated at least once with Sci-B-Vac™ and had at least one post study IP administration follow-up visit. This analysis set will serve as the primary analysis set for efficacy and safety inference.

10.4.2 Full Treatment (FT) Analysis Set

The Full Treatment (FT) analysis set is a subset of the mITT analysis set and will consist of all subjects who were vaccinated 3 times with Sci-B-Vac™ and had at least one visit following the 3rd vaccination.

10.5 SUBJECT DISPOSITION

Data from subjects who are screened but not treated, subjects in the mITT, FT analysis sets, as well as study withdrawal data will be summarized using descriptive statistics. This summary will include all subjects screened into the study. The denominator for calculating the percentages will be the set of the mITT.

10.6 DEMOGRAPHICS AND BASELINE CHARACTERISTICS

Demographic and baseline data as well as disease prognostic factors, medical history and prior medications will be summarized for the mITT analysis set using descriptive statistics. For continuous variables, descriptive statistics (number [n], mean, standard deviation (SD), standard error, median, minimum, and maximum) will be provided. For categorical variables, subject counts and percentages will be provided. Categories for missing data will be presented if necessary. Missing categories will be presented if necessary.

10.7 EFFICACY ENDPOINTS AND ANALYSES

Analyses of primary and secondary efficacy endpoints will use the mITT Analysis Set including all enrolled subjects who were vaccinated at least once with Sci-B-Vac™ and had at least one post first Sci-B-Vac™ administration follow-up visit.

10.7.1 Primary Endpoint Definition and Analysis

The primary endpoint of the study is the Seroprotection rate (SPR), defined as the proportion of subjects with anti-HBs antibody titer at least equal to 10mIU/ml, at Month 7 (i.e. one month after the third immunization with Sci-B-Vac™). Subjects early terminated from the study for any reason at any time while having an anti-HBs antibody concentrations \geq 10mIU/ml will be considered among those who met endpoint.

	Protocol No.: SciB018
	Version and Date: Version 2.0, September 9, 2015 Amendment 1

The principal analysis of the primary endpoint will employ a non-inferiority analysis [SAS PROC FREQ with binomial (noninf margin=0.09 p=(1- α) exact)] statement will be used for testing the below hypothesis:

$$H_0: P-p_0 \leq -\text{Margin}$$

$$H_1: P-p_0 > -\text{Margin}$$

Where p_0 , the assumed true SPR is 95% and the non-inferiority margin is 9.0%, employing that study will be considered successful if the lower bound of the (1- α) exact CI will be 86.0% or more.

10.7.2 Secondary Endpoints and Analyses

The secondary endpoints for the study are:

- SPR at one month after the first injection and at every month until Month 6 inclusive and at months 9 and 12.
- Percentage of subjects with anti-HBs antibodies titer ≥ 100 mIU/ml at Month 0, and then at every month until Month 7 inclusive and at months 9 and 12.
-
- The geometric mean concentration (GMC) as determined by anti-HBsAg antibody titers at Month 0, then at every month until Month 7 inclusive and at months 9 and 12.

SPR at all time points as above defined will be analyzed using the principal analysis method as above defined. The geometric mean concentration (GMC) as determined by anti-HBsAg antibody titers at Month 0, then at every month until Month 7 inclusive and at months 9 and 12 will be displayed across time in order to establish the kinetic of the immunological response during the study.

10.7.3 Exploratory Endpoints and analyses

The exploratory endpoints for the study are:

- The anti-preS1 antibody titers measured at Month 0, then at every month until Month 7 inclusive and at months 9 and 12.
- The anti-preS2 antibody titers measured at Month 0, then at every month until Month 7 inclusive and at months 9 and 12.

The geometric mean concentration (GMC) at Month 0, then at every month until Month 7 inclusive and at months 9 and 12 will be displayed across time in order to establish the kinetic of the immunological response during the study.

10.8 DESCRIPTIVE STATISTICS

All measured variables and derived parameters will be listed individually and tabulated and descriptive statistics will be provided. For categorical variables summary tables will be provided displaying sample size, absolute and relative frequency and percentages. For continuous variables summary tables providing sample size, mean value or geometric means where appropriate, median, standard deviation (SD), standard error, minimum and maximum values. Summary statistics of Anti-HBs antibody concentrations and Anti-PreS1 and Anti-PreS2 antibodies concentrations will use geometric means due to the expected dispersion and skewness of the data.

Descriptive statistics for each of the study endpoints will be provided for the mITT Analysis Set and for both mITT and FT analyses set for the primary endpoint only.

	Protocol No.: SciB018
	Version and Date: Version 2.0, September 9, 2015 Amendment 1

10.9 SAFETY ASSESSMENTS

10.9.1 Treatment Emergent Adverse Events

Adverse events will be recorded from the time when a subject has signed the Informed Consent Form and throughout the study, including the follow-up period. The MedDRA dictionary will be used to standardize the terms used by the investigator to describe the Adverse Events. The following were incorporated into the analyses which will include only Treatment Emergent Adverse Events (TEAEs), namely, events that were started on the day of first study dose or afterwards.

- The incidence (no. of patients) and frequency (no. of events) of TEAEs broken down by SOC and by SOC and Preferred Term according to MedDRA dictionary.
- The incidence (no. of patients) and frequency (no. of events) of TEAEs broken down by events attributes.
- The derived dictionary used in the analyses.
- Listing of SAEs (regardless if started before or after first study dose) of randomized and dosed subjects captured in the clinical database until database drop date.
- Listing of Non-Treatment Emergent AEs.

10.9.2 Vital Signs

Vital signs will be measured at each treatment visit including at unscheduled or early termination visits. Analyses of vital signs were performed in the following manner:

- Box-Plots of vital signs before first study dose and afterwards by scheduled visit will be generated.
- Descriptive statistics of vital signs before first study dose and afterwards as well as the changes from baseline by scheduled visit will be generated.
- The incidence (no. of subjects) of potentially clinically significant (PCS) abnormal values will be summarized in a frequency table and will be listed.

10.9.3 Laboratory Evaluations

Analyses of safety laboratory data will be performed in the following manner:

- Box-Plots of laboratory measurements first study dose and afterwards by scheduled visit will be provided.
- Descriptive statistics of quantitative tests results and changes from baseline by scheduled visit.
- Quantitative laboratory measurements will be categorized with reference to the normal ranges as Low, Normal or High. Shift analysis of the categorical change from baseline to each scheduled visit and to the last observed assessment will also be presented.
- Incidence tables of PCS lab values as well as the individual subject listing will also be provided.

	Protocol No.: SciB018
	Version and Date: Version 2.0, September 9, 2015 Amendment 1

10.9.4 Other Safety Outcome Measures

Summary statistics of other safety evaluations including assessment of local safety evaluations and pain evaluations will be tabulated and listed. Kaplan-Meier curves will be used to describe time to study withdrawal.

10.10 REPORTING DEVIATIONS FROM THE STATISTICAL PLAN

Deviations from the statistical plan, along with the reasons for the deviations, will be described in protocol amendments, the clinical study report, or any combination of these, as appropriate.

10.11 STATISTICAL SOFTWARE

Study accumulated data will be analyzed and summarized using the SAS[®] version 9.3(SAS Institute, Cary North Carolina) or higher.

11 ETHICS

11.1 INSTITUTIONAL REVIEW BOARD OR INDEPENDENT ETHICS COMMITTEE

Prior to initiation of the study, the Investigator will submit the study protocol and amendments, sample ICF, and any other documents that may be requested to the IRB/IEC for review and approval. The Investigator will request that the IRB/IEC provide written approval of the study and will keep on file records of approval of all documents pertaining to this study. The Investigator will not begin the study until the protocol and ICF have been approved by the IRB/IEC. The Investigator must agree to make any required progress reports to the IRB/IEC, as well as reports of SAEs, life-threatening conditions, or death.

11.2 ETHICAL CONDUCT OF THE STUDY

All clinical work conducted under this protocol is subject to GCP guidelines. This includes an inspection by Sponsor or its designee, health authority or IRB/IEC representatives at any time. The Investigator must agree to the inspection of study-related records by health authority representatives and/or Sponsor or its designee.

The study will be conducted in accordance with Sponsor's standards operating procedures and the following guidelines:

- GCP: Consolidated Guideline (International Conference on Harmonisation of Technical Requirements for the Registration of Pharmaceuticals for Human Use, May 1996).
- Declaration of Helsinki: Seoul, 2008
- Israeli Guidelines, Laws and Regulations for the conduct of clinical trials (2006)

11.3 SUBJECT INFORMATION AND CONSENT

Prior to screening for the study each subject will be informed in detail about the study drugs to be administered, and the nature of the clinical investigation with its risks and discomforts to be expected. The basic elements of informed consent as specified by the FDA (21 CFR 50.25) and ICH-GCP will be followed. The subjects will also be instructed that they are free to withdraw their

	Protocol No.: SciB018
	Version and Date: Version 2.0, September 9, 2015 Amendment 1

consent and discontinue their participation in the study at any time without prejudice. Written consent will be obtained from each subject to be involved in the clinical trial by using the IRB/IEC-approved ICF prior to the conduct of any study-related activity. A copy of the ICF will be submitted together with this protocol and must be approved by the IRB/IEC prior to study commencement. Each subject will be given a copy of the written ICF, and each subject's chart will include the signed ICF for study participation. The original subject signed and dated ICFs will be maintained by the site for 15 years. Regulatory authorities may check the existence of the signed ICF in this central study folder if not having done so during the study.

11.4 SUBJECT INSURANCE

A product liability to cover against injury and damages arising from the use of products in this project is provided by SciVac for the total duration of the study covering the subjects and Investigators in respect of the risks involved in conducting this study according to this protocol. The insurance policy will be filed in the Investigator's site file or can be made available to the Investigator and to the IRB/IEC upon request.

Where applicable, subjects will be insured through contract between an insurance company and the Sponsor.

11.5 PERSONAL DATA PROTECTION

SciVac complies with the principle of subject's right to protection against invasion of privacy. Throughout this trial, all subject data will be identified only by a subject identification number and subject initials and date of birth. The data will be blinded in all data analyses. The subject must be informed and consent as required that authorized personnel on behalf of SciVac such as study monitor, auditor etc. and relevant health regulatory agency will have direct access to personal medical data to assure a high quality standard of the study.

At the subject's request, medical information may be given to his or her personal physician or other appropriate medical personnel responsible for his or her welfare.

11.6 INFORMING THE GENERAL PRACTITIONER

The Investigator will inform the subject's primary care physician of the subject's participation in the study, by sending a letter to the physician as required by the Israeli Guidelines for the Conduct of Clinical Trials.

11.7 PROTOCOL EXCEPTIONS AND DEVIATIONS

It is expected that subjects will meet all eligibility criteria as specified in the protocol. Deviations from the protocol should be avoided, unless required for the safety of the subject. Protocol deviations, and if possible the reason for occurrence, will be documented by the study monitor and will be included in the final clinical study report. The Investigator must report any protocol deviation to the Sponsor and if required, to the IRB/IEC in accordance with local regulations, within reasonable time.

11.8 PROTOCOL AMENDMENTS

All protocol modifications must be submitted to the site IRB/IEC in accordance with local requirements and, if required, to the Regulatory Authority, either as an amendment or a notification.

1. ABBREVIATIONS

Abbreviation/Term	Definition
AE	Adverse Events
ANA	Antinuclear antibodies
ALT	Alanine transaminase
Anti-HBc	Antibodies to hepatitis B core antigen
Anti-HBs	Antibodies to HBsAg
Anti-HCV	Antibodies to hepatitis C virus
AST	Aspartate aminotransferase
BMI	Body Mass Index
BP	Blood Pressure
BUN	Blood Urea Nitrogen
CBC	Complete Blood Count
cm	Centimeter
CRC	Clinical Research Center
CRF	Case Report Form
ECG	Electrocardiogram
FDA	Food and Drug Administration
GCP	Good Clinical Practice
GGT	Gamma glutamyl transferase
GLP	Good Laboratory Practice
GMP	Good Manufacturing Practice
GMR	Geometric mean ratio
GSK	Glaxo Smith Kline
h	Hours
HbsAg	Hepatitis B Surface Antigen
HIV	Human immunodeficiency virus
HR	Heart Rate
ICF	Informed Consent Form
ICH	International Conference on Harmonization
IEC	Independent Ethics Committee
IM	Intramuscular
IMP	Investigational Medicinal Product
IRB	Institutional Review Board
Kg	Kilogram
m	Meter
MedDra	Medical Dictionary for Regulatory Activities
mg	Milligram
min	Minute
mITT	Modified intention-to-treat analysis
ml	Milliliter
MOH	Ministry of Health
N/A	Not Applicable
°C	Degrees centigrade
PI	Principal Investigator
PT	Prothrombin Time
PT	Preferred Term

PT/INR	Prothrombin time/International Normalized Ratio
QA	Quality Assurance
R&D	Research and Development
RBC	Red blood cells
RDW	RBC distribution width
RR	Respiration rate
SAS	Statistical Analysis Software
SAE	Serious Adverse Event
SOC	System Organ Class
SOP	Standard Operation Procedures
SPR	Seroprotection rate
SUSAR	Suspected unexpected serious adverse reaction
TASMC	Tel Aviv Sourasky Medical Center
TEAE	Treatment emergent adverse events
WBC	White blood cell
WHO	World Health Organization
µg	Microgram

2. INTRODUCTION

2.1 Objectives

This document details the statistical analysis that will be performed for the SciVac Ltd. Phase IV study SciB018.

The study primary objective is:

- To validate the new in-house reference standard vaccine for routine quality control purposes, in compliance with the European Pharmacopeia and the Israeli Ministry of Health.

The secondary objectives are:

- To characterize the immunological response throughout the study.
- To monitor the subjects for safety throughout the study period

The Exploratory Objectives are:

- To collect blood samples for the in vitro validation of anti-HBs, anti-preS1 and anti-preS2 antibodies assays.
- To assess the anti-preS1 and anti-preS2 antibodies responses upon vaccination.
- To investigate additional protective mechanisms of action and the type of immune response triggered by the vaccination. No genetic tests will be performed.

2.2 Design

This will be a post-marketing, open-label, single arm study in healthy volunteers who had never been vaccinated with any hepatitis B vaccine and who are HBs antigen, anti-HBc and anti-HBsAg antibodies seronegative.

The study assessments will be performed as described in the study flow chart (See section 2.3).

This study will consist of three periods:

Screening Period (Visit 1: up to 1 month prior to first vaccination)

After signing of the informed consent form (ICF), screening procedures will be carried out as specified in the study protocol.

Treatment and Follow-up Period (Visits 2-8: Months 0-6)

Subject identification number will be assigned to all eligible subjects following assessment of inclusion and exclusion criteria.

All eligible subjects will receive Sci-B-Vac™ vaccine. The treatment phase will include three I.M. doses of Sci-B-Vac™ administered in the deltoid muscle on Month 0, Month 1, and Month 6. Subjects will be followed up for safety evaluations and for efficacy (by anti-HBs, anti-pre-S1 and anti-pre-S2 testing), every month. The previous injection site will be inspected before the second and third administration.

The following assessments will be performed during each treatment visit: recording of AEs and concomitant medications, vital signs and blood tests for quantitative anti-HBs, anti-preS1 and anti-preS2 antibodies and safety assessment (including blood and urine laboratory tests).

Female subjects will also undergo a urine pregnancy before each injection. Vital signs are not required on follow-up visits when vaccine is not administered.

Post-Vaccination Follow-up Period (Visits 9-11: Months 7, 9 and 12)

Additional subject follow-up visits will take place 1, 3 and 6 months after the last vaccine administration. On each visit, subjects will be inquired about AEs and concomitant medications, and blood samples for quantitative anti-HBs, anti-preS1 and anti-preS2 antibodies levels will be drawn. The last visit (Month 12) is a study termination visit in which all subjects will also undergo physical examination, laboratory safety assessments (CBC, blood chemistry and urinalysis), vital signs measurement and a 12-lead ECG. In addition, female subjects will undergo a urine pregnancy test.

2.3 Study Flow-chart

Visit Number	1	2	3	4	5	6	7	8	9	10	11
Visit Name	Screening	Treatment 1	Treatment 2	Follow-up	Follow-up	Follow-up	Follow-up	Treatment 3	Follow-up	Follow-up	Study Termination
Month (Week) of the Study	-1 ((-4) - 0)	0 (0 ¹)	1(4 ¹)	2(8 ¹)	3(12 ¹)	4(16 ¹)	5(20 ¹)	6(24 ¹)	7(28 ¹)	9(36 ²)	12(48 ²)
Activity											
ICF	X										
Demographics	X										
Inclusion/Exclusion	X	X									
Medical history	X										
Vital signs ³	X	X ⁴	X ⁴					X ⁴			X
Smoking status	X										
Weight, height, BMI	X										
Physical examination	X										X
Blood safety tests ⁵	X	X ⁶	X ⁶					X ⁶			X
Screening serology ⁷	X ⁸										
General urinalysis	X	X ⁶	X ⁶					X ⁶			X
Serum β-HCG	X										
Urine pregnancy test		X ⁶	X ⁶					X ⁶			X
12-lead ECG	X										X
Sci-B-Vac™ injection ⁹		X	X					X			
Local reaction grading		X ¹⁴	X ^{14,15}	X ¹⁵				X ¹⁴	X ¹⁵		
Serologic markers for hepatitis B infection	X ^{8,10}	X ^{6,11}	X ^{6,11}	X ¹¹	X ¹¹	X ¹¹	X ¹¹	X ^{6,11}	X ¹¹	X ¹¹	X ¹²
Serologic response to immunization ¹³		X ⁶	X ⁶	X	X	X	X	X ⁶	X	X	X
Sample for further investigations		X ⁶	X ⁶	X	X	X	X	X ⁶	X	X	X
Adverse Events	Recorded throughout the study										
Concomitant Medications	Recorded throughout the study										

- 1 \pm 3 days (Visit2/Treatment 1 may be performed up to 4 weeks +3 days from screening visit)
- 2 \pm 8 days
- 3 Sitting BP, HR, RR, oral temperature
- 4 Within 60 min before vaccine administration and at 60 (\pm 15) min after vaccination
- 5 CBC, blood chemistry, PT/INR (screening only) - see Appendix B
- 6 Prior to vaccine administration
- 7 Anti HIV (Ab type 1&2), anti-HCV Ab, anti-HAV IgM antibodies, ANA (See Appendix B)
- 8 Positive serology excludes from participation in the study
- 9 One IM injections of 1.0 ml into the deltoid muscle. The previous injection site will be inspected before the second and third administration. Subjects will remain for observation in the CRC for at least 1 hour after injections.
- 10 HBsAg, anti-HBs antibodies (also markers for previous vaccination), total anti-HBc antibodies and IgM anti-HBc antibodies.
- 11 HBsAg only.
- 12 HBsAg, Total anti-HBc antibodies and IgM anti-HBc antibodies
- 13 Anti-HBsAg, anti-preS1 and anti-preS2 antibodies
- 14 Local reaction grading after vaccination
- 15 Local reaction grading of previous vaccine administration and follow up until symptoms resolve

2.4 Study Populations

Up to ninety two (92) healthy subjects will be enrolled in the study

Intent-to-Treat (ITT) Population includes all enrolled subjects who were vaccinated at least once with Sci-B-Vac™. The Safety population will be same as ITT population.

Modified Intent-to-Treat (mITT) population is a subset of the ITT set. This set will consist of all enrolled subjects who were vaccinated at least once with Sci-B-Vac™ and had at least one post vaccination follow-up visit, fully comply with the study protocol, had no violation of any of the inclusion/exclusion criteria and did not demonstrate an anamnestic response after the 1st administration of Sci-B-Vac. An anamnestic response revealed by Sci-B-Vac is defined as anti-HBs level above 6000mIU/ml (the highest titer recorded upon Sci-B-Vac 1st injection) in a subject with no detectable anti-HBs antibody at visits 1 and 2. Subjects who early terminated the study but reached the primary endpoint will be included as well. Subjects who did not complete the full-course of vaccination (i.e. 3 injections) and did not reach SPR will be excluded from the mITT set. This analysis set will serve as the primary analysis set for efficacy and safety inference.

Full Treatment (FT) set is a subset of the mITT analysis set and will consist of all subjects who were vaccinated 3 times with Sci-B-Vac™ and had at least one visit following the 3rd vaccination.

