2.7 Interim Analyses

The percent of subjects who achieved the primary endpoint will be tested at various time points. As soon as approximately 95% of the subjects (from at least 50 subjects) will be found seroprotected (having anti-HBs antibody concentrations $\geq 10\text{mIU/ml}$) then the primary efficacy endpoint will be achieved and the analysis will be considered a formal interim analysis and will be reported. A second interim analysis will be performed after all subjects have completed all three injections. Subjects who early terminated the study but reached the primary endpoint prior to termination will be included in the analysis.

Interim analysis reports will include all efficacy and safety information collected up to the interim analysis cut-off date. Exploratory endpoints (anti-pre-S1 and anti-pre-S2 testing) will not be included in the interim reports.

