4.4 Primary Endpoint Analysis

The primary endpoint of the study is the Seroprotection rate (SPR), defined as the proportion of subjects with anti-HBs antibody titer at least equal to 10mIU/ml, at Month 7 (i.e. one month after the third immunization with Sci-B-Vac™). In the first Interim Analysis the primary endpoint will be tested on month 4. Subjects early terminated from the study for any reason at any time while having an anti-HBs antibody concentrations ≥ 10 mIU/ml will be considered among those who met endpoint.

The principal analysis of the primary endpoint will employ a non-inferiority analysis [SAS PROC FREQ with binomial (noninf margin=0.09 p=(1- α) exact)] statement will be used for testing the below hypothesis:

H0: $P-p_0 \leq -\text{Margin}$

H1: $P-p_0 > -\text{Margin}$

Where p_0 , the assumed true SPR is 95% and the non-inferiority margin is 9.0%, employing that study will be considered successful if the lower bound of the (1- α) exact CI will be 86.0% or more.

The rate of responders will be calculated along with 95% confidence interval using Exact binomial method. The final population for statistical analysis will include only subjects who fully comply with the study protocol, have no inclusion/exclusion criteria violation and subjects who early terminated the study but reached the primary endpoint prior to withdrawal (mITT population).

Comparative analysis will be applied for baseline characteristics (such as gender, smoking status, age and BMI) between non seroprotected subjects (i.e. anti-HBsAg antibody<10), seroprotected subjects (ie. anti-HBsAg antibody ≥ 10 mIU/ml) and subjects with Anti-HBs ≥ 100 mIU/ml.

Age categories will be defined by intervals of 5 or 10. BMI will be defined <25 or ≥ 25 . Smoking status will be defined using 5 categories:

Never

Past-smoker;

Light smoker (up to 10 cigs/day)

Moderate smoker (10-19 cigs/day)

Heavy smoker (20 or more cigs/day) BMI categories will be defined <25 and ≥ 25

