5. APPENDIX I: TABLES TO BE INCLUDED IN THE STATISTICAL REPORT

Table number	Table Title
14.1	Demographic and Baseline Data
14.1-1.1	Disposition of subjects
14.1-1.2	Primary reason for early discontinuation
14.1-2.1	Analysis population
14.1-3.1	Demographic and Baseline data, ITT
14.1-4	Medical History, ITT
14.1-5	Baseline Physical Examination, ITT
14.1-6	Any Concomitant Medication, ITT
14.1-7	Any Concomitant Non-drug Medication, ITT
14.1.2	Exposure to Sci-B-Vac injection
14.1.2.1	Sci-B-Vac injection, ITT
14.2	Efficacy Analysis
14.2-1	Seroprotection rate (SPR) by Month, mITT
14.2-2	Seroprotection rate (SPR) by Month, FT (for first IA mITT who completed month 7 will be presented)
14.2-3	Secondary Endpoint Analysis: Percentage of Subjects with Anti-HBs \geq 100 mIU/ml by Month, mITT
14.2-4	Secondary Endpoint Analysis: Percentage of Subjects with Anti-HBs \geq 100 mIU/ml) by Month, FT (for first IA mITT who completed month 7 will be presented)
14.2-5	Geometric means of anti-HBs antibody titers by month, mITT
14.2-6	Geometric means of anti-HBs antibody titers by month, FT (for first IA mITT who completed month 7 will be presented)
14.2-7	Frequency of gender by responders (SPR) (at month 4 for first IA)
14.2-8	Frequency of age categories by responders (SPR) (at month 4 for first IA)
14.2-9	Frequency of Responders (SPR) by Smoking status and month (month 4 for IA)
14.2-10	Frequency of Responders (SPR) by BMI categories and month (at month 4 for first IA)
14.2-11	Geometric means of anti-HBs antibody titers by month and Gender
14.2-12	Geometric means of anti-HBs antibody titers by month and age categories
14.2-13	Geometric means of anti-HBs antibody titers by month and Smoking status
14.2-14	Geometric means of anti-HBsAg antibody titers by month and BMI categories
14.2-15	Serologic Markers for Hepatitis B Infection, ITT
14.3	Safety Data
14.3.1	Adverse Events
14.3.1	Summary Incidence of TEAE (Treatment Emergent Adverse Events), ITT
14.3.1-1	Summary of Adverse Events by SOC and PT, ITT

Table number	Table Title
14.3.1-2	Summary of Adverse Events by SOC and PT and Severity, ITT
14.3.1-3	Summary of Adverse Events by SOC and PT and Relation to study drug, ITT
14.3.1-4	Summary of Serious Adverse Events by SOC and PT, ITT
14.3.2	Listing of SAEs (if applicable)
14.3.2-1	Listing of Serious Adverse Events
14.3.4	Abnormal Laboratory Results
14.3.4-1	Incidence of Hematology Abnormal Clinically Significant Results
14.3.4-2	Out of Range Hematology Results

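### At the Month 4 first interim, the SAP's incomplete-course exclusion removes continuing subjects below 10 mIU/ml who have not yet had dose 3, which biases the mITT seroprotection rate upward

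*SAP*

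**What the plan says.** SAP 2.4 defines the mITT and adds this exclusion: "Subjects who did not complete the full-course of vaccination (i.e. 3 injections) and did not reach SPR will be excluded from the mITT set". Of the mITT it says: "This analysis set will serve as the primary analysis set for efficacy and safety inference". The mITT definition in section 10.4.1 of protocol version 2.0 has no such exclusion, so the clause comes from the SAP alone.

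On timing, SAP 2.2 schedules "three I.M. doses of Sci-B-Vac™ administered in the deltoid muscle on Month 0, Month 1, and Month 6". SAP 4.4 states: "In the first Interim Analysis the primary endpoint will be tested on month 4". SAP 2.7 makes the look a formal interim, with the primary endpoint counted as achieved, "As soon as approximately 95% of the subjects (from at least 50 subjects) will be found seroprotected". It then adds: "A second interim analysis will be performed after all subjects have completed all three injections".

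In SAP Appendix I, Table 14.2-1 is "Seroprotection rate (SPR) by Month, mITT", with no adaptation for the first interim. Table 14.2-2 is adapted: "Seroprotection rate (SPR) by Month, FT (for first IA mITT who completed month 7 will be presented". So at the first interim some subjects are expected to be past dose 3.

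**The concern.** A continuing subject who has given the Month 4 sample but has not reached Month 6 has had two injections because the schedule says so. If that subject has not reached 10 mIU/ml, both conditions of the exclusion are met and the subject leaves the denominator. A subject at the same stage at or above 10 mIU/ml stays. Membership of the primary efficacy set then depends on the outcome being estimated, among people who have missed nothing.

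At stake is the first-interim seroprotection rate (SPR), the set to which the 86% exact limit is applied, and possibly the declaration that the primary endpoint has been achieved. The rule also sits badly with the SAP's own outputs. SAP 4.4 compares baseline characteristics of non-seroprotected and seroprotected subjects, and Tables 14.2-7 to 14.2-10 make the responder breakdowns at Month 4 for the first interim. As worded, the exclusion removes some or all of the non-seroprotected group.

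**Working it through.** **The plan's own limit.** SAP 2.6 gives n = 70, an expected SPR of 0.95 and a lower bound of 86.0% or more. The exact (Clopper-Pearson) lower limit is the α-quantile of Beta(x, n − x + 1). For 66/70 = 94.3% the two-sided 95% limit is 86.01%, so the figure is reproduced. For 65/70 it is 84.1%, which fails. The one-sided 95% limit at 66/70 is 87.4%, which also satisfies the statement. The two-sided limit is used below.

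**Inputs from the documents.** Month 4 is Week 16, dose 3 Week 24 and Month 7 Week 28 (SAP 2.3). The trigger is about 95% of at least 50 subjects (SAP 2.7). The success limit is 86.0% (SAP 2.6 and 4.4).

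**Assumptions, because the documents give no figure.**
- n = 84 subjects with a Month 4 result. This is the protocol's enrolment figure; SAP 2.4 allows up to 92.
- True Month 4 SPR p = 80% or 90%.
- n₃ = number already given dose 3 at the cut: one quarter (21), one third (28) or one half (42). One third is what even spacing of subjects between Week 16 and Week 28 would give: (28 − 24)/(28 − 16).
- A subject below 10 mIU/ml at Month 4 without dose 3 has not reached 10 mIU/ml at any other visit.
- The trigger is applied to the mITT.

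**Formulas.** Let x₃ and x₂ be the Month 4 responders with and without dose 3.
- As worded: SPR = (x₃ + x₂)/(n₃ + x₂)
- All counted: SPR = (x₃ + x₂)/n

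With expected counts at p = 80%, x₃ + x₂ = 67.2:
- n₃ = 21: 67.2/(21 + 50.4) = 67.2/71.4 = 94.1%
- n₃ = 28: 67.2/(28 + 44.8) = 67.2/72.8 = 92.3%
- n₃ = 42: 67.2/(42 + 33.6) = 67.2/75.6 = 88.9%
- all counted: 67.2/84 = 80%

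At p = 90% the same steps give 75.6/77.7 = 97.3%, 75.6/78.4 = 96.4% and 75.6/79.8 = 94.7%, against 90%.

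**Probability of meeting the trigger.** With x₃ ~ Bin(n₃, p) and x₂ ~ Bin(n − n₃, p), sum over all outcomes with SPR of at least 95% and a denominator of at least 50:

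| Share given dose 3 | p = 80% | p = 90% |
|---|---|---|
| one quarter | 0.37 | 0.87 |
| one third | 0.16 | 0.75 |
| one half | 0.02 | 0.50 |
| all subjects counted | 0.0001 | 0.07 |

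At p = 80% with one quarter dosed, the two-sided exact lower limit reaches 86% with probability 0.53, against 0.0003 with everyone counted.

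**The extreme case.** If no Month 4 non-responder in the set has had dose 3, then n₃ adds no failures and the SPR is 100% for any p. For example, 67/67 (lower limit 94.6%) replaces 67/84 = 79.8% (lower limit 69.6%). If every Month 4 non-responder has had dose 3, there is no inflation.

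**The case against.** The strongest reply is that the clause was meant for leavers. It follows directly on a sentence that keeps early-terminated subjects who reached the endpoint, and the two read as a pair. The planned Month 4 responder comparisons point the same way. This is a fair account of intent. But the preceding sentence names early termination and the exclusion does not, and a programmer coding the set flag works from the text.

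A second reply is that a fully literal reading would take reaching SPR to mean the Month 7 endpoint. Nobody before dose 3 would then qualify and responders would be excluded too. That reading empties the interim set of everyone before dose 3, so it is not workable at a Month 4 test. It is a further reason to reword.

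A reader might infer that the rule removes every continuing non-responder and forces the interim SPR to 100%. The documents do not support that. Appendix I expects some first-interim subjects to have completed Month 7, and their Month 4 failures stay in the denominator. The exclusion names no visit, so a subject below 10 mIU/ml at Month 4 who reached it at another monthly visit may also stay.

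Nor is the trigger sure to be met. SAP 2.7 names no analysis set for it; Appendix I ties the mITT to tables only. The 50-subject floor can also work against it: with 60 subjects, a true 80% and nobody dosed, the trigger is met with probability 0.32, because the exclusion shrinks the denominator.

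Finally, the effect on continuing subjects is confined to the first interim. Section 10.1 of the protocol describes an interim for possible early termination, but SAP 2.7 states no stopping action.

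**Conclusion.** The point holds in a limited form. As worded, SAP 2.4 selects on the outcome among continuing subjects at the first interim and biases the mITT SPR upward. With one quarter to one half already given dose 3, a true 80% is reported on average as about 94% to 89%, and a true 90% as about 97% to 95%. If the trigger is applied to the mITT, it is met far more often than it should be, most clearly at a true 90% (0.87 to 0.50 against 0.07). At a true 80% with half dosed, the trigger probability stays small (0.02).

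These sizes rest on an assumed n, p and share dosed, none of which the documents give. The direction does not: inflation vanishes only if each Month 4 non-responder either has had dose 3 or reached 10 mIU/ml at another visit. By the second interim and the final analysis continuing subjects have had dose 3, so the clause then touches only leavers.

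**What to change.** - **SAP 2.4:** limit the exclusion to subjects who permanently left the study before completing three injections. State that continuing subjects not yet due for dose 3 stay in the mITT at any interim cut.
- **SAP 2.7 and 4.4:** name the set for the first-interim trigger. State that the trigger and the Month 4 SPR use as denominator all mITT subjects with a Month 4 anti-HBs result, including those below 10 mIU/ml. Tables 14.2-1 and 14.2-7 to 14.2-10 should follow the same rule.
- **If the first interim has already been run:** state in the report which denominator was used.

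The cost is a few sentences and a changed set flag in the interim program. The interim SPR may look less favourable. If the exclusion was always meant for leavers only, the results do not change.
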